#### **8.1.2. Sensitivity Analysis**

Sensitivity analyses of the primary variable will be performed for the ITT Set in the following ways:

1. Repeating the primary analysis using Fisher's exact test.
2. The same logistic regression methods but applying the Worst Observation Carried Forward (WOCF) imputation method for missing values when there are less than 20 days of reported data in the eDiary. Specifically, this will use a patient's worst-case observation within the 28-day period to populate the missing values within that time period.
3. The same logistic regression methods will be re-calculated on "observed data" (ie, without imputation for missing counts when there are less than 20 days of reported data).

A sensitivity analysis will also be performed for the PRO variables to determine if there is a difference in the imputed data versus the observed data. Continuous data will be analyzed with a t-test and Fisher's exact test will be used for the categorical data.

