7.3.2 Secondary Efficacy Analyses

A sensitivity analyses of the primary variable will be performed using (1) Fisher's exact test based on the imputation method discussed in the SAP, and (2) using a similar logistic regression analysis but applying another imputation scheme (to be discussed in the SAP) to impute for missing values when there are less than 20 days of reported data in the e-diary. Other sensitivity analyses will be described in the SAP.

The 3 secondary efficacy variables (Section 7.2.2) are ranked in a hierarchical order of clinical importance. To control for Type I error rate for multiple secondary endpoints, a hierarchical testing gatekeeping procedure will be used, starting with the first secondary endpoint in the ranking order, followed by the next, and so on, in a sequential fashion. If the test of the first secondary endpoint shows statistical significance at the 0.05 level (2-sided), then there is justification to proceed to test the next endpoint in the ranking order; this stepwise process continues for all the endpoints listed in the hierarchical order. However, if no statistical significance is shown at the 0.05 level (2-sided) for the test of any specified endpoint in the hierarchical order, then that endpoint and all subsequent endpoints below this in the ranking order should not be considered statistically significant, regardless of their nominal p-value.

The change from baseline in frequency of headache days will be compared between BOTOX and topiramate groups via analysis of covariance (ANCOVA) with baseline headache day count as the covariate. A treatment-by-investigator site interaction will also be investigated in a separate ANCOVA model.

The HIT-6 score will be compared between treatment groups using a nonparametric rank analysis of covariance (rank ANCOVA) (Stokes et al, 2000), with treatment as a factor, and adjusting for the baseline value.

The $\geq 70\%$ responder rate will be analyzed similar to the primary endpoint, using a logistic regression model adjusted by the baseline frequency of headache days. The exact conditional logistic regression analysis will be performed if there are convergence issues with the default unconditional analysis.

[REDACTED]

[REDACTED]

[REDACTED]

[REDACTED]

[REDACTED]

[REDACTED]

[REDACTED]

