#### 4.1. Sample Size

Approximately 400 patients (200 per arm) are required to provide 90% statistical power to detect an expected treatment difference of 16%. This calculation assumes a topiramate responder rate of 28% and a BOTOX responder rate of 44% at the primary timepoint of Week 32. A responder is defined as having a  $\geq 50\%$  decrease from baseline in the frequency of headache days per 28-day period. The above calculations were based on a 2-sided test at  $\alpha = 0.05$ , using the commercial software nQuery Advisor version 6.01, procedure PTT1 for a two-group continuity corrected Chi-squared test of equal proportions, with equal sample sizes.

The assumed responder rate for BOTOX was estimated from 2 Allergan Phase 3 double-blind, placebo-controlled studies which reported observed rates of 43.5% (113/260), 50.5% (141/279), and 47.1% (254/539) for Study 191622-079, Study 191622-080, and their pooled/combined data, respectively, at the primary timepoint of Week 24 (Aurora et al, 2010; Diener et al, 2010). At Week 32, the observed rates were 55.7% (141/253), 61.7% (161/261), and 58.8% (302/514), respectively. The corresponding rates for the Intent-To-Treat (ITT) analysis where patients who terminated from the study were treated as failures were reported as 41.3% (141/341), 46.4% (161/347), and 43.9% (302/688), respectively. Based on these 2 studies, the BOTOX responder rate for an ITT analysis at Week 32 ranged from 41.3% to 46.4%, and the value of 44% was chosen as reasonable for the purposes of sample size calculation for the current study.

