## **4.2. Randomization, Stratification, and Blinding**

On Day 1, qualified patients will be randomly assigned at a 1:1 treatment allocation ratio to 1 of 2 treatment arms: 155 U BOTOX given IM or up to 100 mg/day of oral topiramate.

Randomization is not stratified for this study.

At the screening visit, once informed consent is obtained, the site staff will log onto the interactive web response system (IWRS) to obtain a unique patient number, which will be used as identification for the electronic patient eDiary, electronic case report form (eCRF), electronic clinical outcomes assessments (eCOA), and all source documentation throughout the study.

The IWRS system will provide the site with the treatment assignment to which the patient is assigned. Sites will dispense study medication according to the IWRS instructions. Sites will log onto the IWRS at subsequent visits to log dispensing of additional study medication as needed. Sites will receive the IWRS confirmation notifications for each transaction. All notifications are to be maintained with the study source documents.

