#### **8.1.1. Primary Analysis**

##### *Missing data*

If there are at least 20 days for which the patient has reported headache data (for either headache days or headache-free days), but less than 28 days in a diary period, the data for counts will be prorated accordingly and rounded to the nearest whole number. The prorating will be based on the number of days with reported data in that period.

For example, if there are 24 days with reported data in a 28-day diary window, the headache day count will be multiplied by  $28/24$  and rounded to a whole number. If the patient reported total daily headache durations that indicated 16 headache days and 8 headache-free days, the patient's standardized counts after prorating by  $28/24$  would be 19 headache days and 9 headache-free days.

If a patient reports eDiary data for less than 20 days in a 28-day period, the patient's entries for this time period will be set to missing.

A baseline observation carried forward (BLOCF) method will be utilized to impute missing values for the primary analysis. This type of imputation replaces the missing value with the baseline value; thus, if a patient has a missing entry for any reason (eg, discontinuation due to AE, lost to follow-up, lack of efficacy), the baseline value data will be utilized and the patient will be considered a nonresponder. Patients who discontinue BOTOX and patient randomized to topiramate who discontinue treatment and subsequently receive BOTOX will be considered nonresponders for the primary and secondary analyses and thus baseline value data will be utilized.

BLOCF will also be used to impute missing values for the PRO analyses.

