#### *Analysis method*

The primary null hypothesis is that BOTOX and topiramate are equally effective, as measured by the proportion of patients with a  $\geq 50\%$  decrease from baseline in the frequency of headache days per 28-day period at Week 32. The alternative hypothesis is that BOTOX has a different effect than topiramate.

The primary comparison between treatment arms will be performed using a logistic regression model, adjusted by the baseline number of headache days as a covariate. The treatment effect will be summarized using an adjusted odds ratio and 95% Wald confidence limits. The p-value from the Wald Chi-square test will also be reported. A 2-sided test with a p-value less than or equal to 0.05 will be considered as statistically significant. All centers will be pooled for this analysis.

The primary analysis will be repeated for the PP and ssITT Sets, if appropriate.

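### SAP 8.1.2 item 2 (worst observation carried forward) gives no value for an empty diary window and can create spurious responders from very sparse ones

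*SAP*

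**What the plan says.** SAP 8.1.1 (Missing data) prorates a 28-day period with 20 to 27 reported days. The treatment of sparser periods begins "If a patient reports eDiary data for less than 20 days in a 28-day period": the period is set to missing, the baseline count is carried forward, and the patient is a nonresponder.

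Protocol 7.3.2 announces a sensitivity analysis "applying another imputation scheme (to be discussed in the SAP) to impute for missing values when there are less than 20 days" of reported data. SAP 8.1.2 item 2 supplies the scheme. It keeps the logistic regression but, for those same sparse periods, uses the patient's "worst-case observation within the 28-day period to populate the missing values within that time period". Item 1 is Fisher's exact test, and item 3 is an analysis of observed data without imputation.

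Discontinuation is handled separately. SAP 3.4 makes early discontinuers of either drug nonresponders. SAP 8 and 8.1.1 repeat this for topiramate patients who switch to BOTOX, and 8.1.1 also for BOTOX discontinuers, but word it for the primary and secondary endpoints or analyses. The SAP does not say in terms whether the rule also governs the sensitivity analyses.

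**The concern.** A period with zero entries meets the trigger of fewer than 20 days, but the replacement value is to come from inside that empty period. The programmer would have to choose between nonresponse, exclusion and a value from another period, and the choice changes the result.

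Where there are 1-19 entries, the method's name suggests a harsher test than the primary analysis. In fact the primary rule already gives every such patient the worst outcome. A patient whose few entries are all headache-free has a headache-free day as the worst observation, so every missing day is filled as headache-free.

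At stake is the robustness evidence for an open-label comparison in which discontinuation follows different paths by arm: patients who stop BOTOX leave the study, while those who stop topiramate stay on and keep the diary. Item 1 does not change the missing-data assumption and item 3 removes patients without a count. That leaves item 2 as the only sensitivity analysis of the primary endpoint that replaces missing values differently.

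**Working it through.** **Plan's own figure.** The sample size rests on 28% versus 44% responders with "procedure PTT1 for a two-group continuity corrected Chi-squared test of equal proportions", two-sided 0.05 and 90% power.
- Uncorrected: n = [1.960·√(2·0.36·0.64) + 1.282·√(0.28·0.72 + 0.44·0.56)]² / 0.16² = 187.05, so 188 per arm.
- Corrected: (187.05/4)·[1 + √(1 + 4/(187.05·0.16))]² = 199.35, so 200 per arm, as stated. Nothing below changes this.

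**Inputs.** Baseline headache days B = 15 to 28 (Protocol 4.3, criterion 3). Reported days k = 0 to 19 (SAP 8.1.1 and 8.1.2). Reported days that meet the headache-day definition h = 0 to k. A responder has a count of at most B/2.

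**Rules.**
- BLOCF: count = B, so always a nonresponder.
- WOCF, k = 0: no observation in the window, so no value.
- WOCF, k = 1-19: count = 0 if h = 0; otherwise h + (28 − k).

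**Enumeration for k = 1-19.** There are 14 baselines and, summing k + 1 over k = 1 to 19, 209 pairs (k, h): 14 × 209 = 2,926 patterns.

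| | Patterns |
|---|---|
| Responder under BLOCF | 0 |
| Responder under WOCF | 321 |
| of which h = 0 | 14 × 19 = 266 |
| of which h ≥ 1 | 55 |
| Same result under both rules | 2,605 |

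The 55 need B ≥ 20 and k ≥ 15. For example, B = 20, k = 19, h = 1 gives 1 + 9 = 10, a responder; h = 2 gives 11, a nonresponder. These counts are not probabilities.

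**How often a sparse diary misleads.** Assume independent days and B = 20.
- No true change, daily risk 20/28: responder with probability 8/28 = 0.29 at k = 1, (8/28)³ = 0.02 at k = 3, and about 0 at k ≥ 10.
- True 70% reduction, daily risk 6/28: 0.79 at k = 1, 0.09 at k = 10 and 0.06 at k = 19.

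So the spurious responders come from very sparse diaries, while a patient with a real 70% reduction and 10 or more entries is mostly called a nonresponder.

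**Effect on the contrast.** Take the planning rates, 88/200 versus 56/200: unadjusted OR = (88·144)/(112·56) = 2.02, Wald p = 0.0009. The numbers of conversions to responder are assumed.

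| Extra responders | OR | p |
|---|---|---|
| 5 BOTOX only | 2.24 | 0.0001 |
| 5 topiramate only | 1.79 | 0.005 |
| 10 in each arm | 1.95 | 0.001 |
| 10 topiramate only | 1.60 | 0.024 |
| 13 topiramate only | 1.49 | 0.052 |

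**Effect of the unstated choice for empty windows.** Counting them as nonresponse leaves the OR at 2.02. Dropping 10 (assumed) from BOTOX gives (88·144)/(102·56) = 2.22. Dropping 10 from topiramate gives (88·134)/(112·56) = 1.88.

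**The case against.** The strongest reply is that nonresponse is the floor of a binary endpoint. Any alternative, including multiple imputation, can only move imputed patients towards response, so leniency is no defect peculiar to WOCF. That stands. WOCF is also stricter than simply prorating the sparse diary: proration would call 1,180 of the 2,926 patterns responders, and all 321 WOCF responders are among them.

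A reader might infer that item 2 cannot challenge the primary result, or that it favours BOTOX. The documents do not support that. The test compares two arms, and conversions on topiramate erode the difference; 13 of them alone would take p above 0.05 at the planning rates. The observed-data analysis can also move either way.

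A reader might also size the problem from the planning studies: 688 − 514 = 174 of 688 BOTOX patients (25%) and 170 − 116 = 54 of 170 topiramate patients (32%) without a value. These are not estimates of empty diary windows here. They come from other trials, and the double-blind topiramate study in the same section gives 13/95 (14%) and 12/96 (12.5%). In this trial most discontinuers are nonresponders by rule, and topiramate switchers keep completing the diary.

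Finally, two clarifying sentences would make WOCF workable. That is true as a minimum, but it would leave the missing-data assumption untested by arm.

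**Conclusion.** The point holds in limited form. As written, item 2 has no value for an empty Weeks 29-32 window. It is never stricter than BLOCF for 1-19 entries, and it turns one or more headache-free entries with nothing else reported into a 100% reduction. The rules differ in 321 of 2,926 patterns, 266 of them of that kind, and agree in the other 2,605. The visible text contains no analysis that varies the missing-data assumption systematically by arm; part of the SAP is blacked out.

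The enumeration assumes that the worst observation is applied day by day to headache-day status. The probabilities assume independent days and B = 20, and the odds ratios are unadjusted with assumed conversions. The number of patients with 0-19 entries is not in the documents, so no effect on the trial's conclusion is shown. This is a defective robustness check, not a flaw in the primary analysis.

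**What to change.** Replace item 2 with multiple imputation of the Weeks 29-32 headache-day count, by arm, from baseline and earlier 28-day periods, for ITT patients with fewer than 20 reported days, including zero. Keep treatment discontinuers as nonresponders in both arms, and state that this rule also governs the sensitivity analyses. Add a tipping-point analysis that varies the assumed response of patients with missing counts separately in each arm.

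If WOCF is kept, state that an empty window counts as nonresponse and that missing days count as headache days even when all reported days are headache-free.

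The cost is SAP wording and some extra programming on data already collected. Because discontinuers stay fixed, the new analysis mainly varies the outcome of patients still on treatment with sparse or empty diaries; if they are few, it will change little.

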## 8.2. Secondary Efficacy Endpoints

The 3 secondary efficacy variables are ranked in a hierarchical order of clinical importance. To control for Type I error rate for multiple secondary endpoints, a hierarchical testing gatekeeping procedure will be used, starting with the first secondary endpoint in the ranking order, followed by the next, and so on, in a sequential fashion. If the test of the first secondary endpoint shows statistical significance at the 0.05 level (2-sided), then there is justification to proceed to test the next endpoint in the ranking order; this stepwise process continues for all the endpoints listed in the hierarchical order. However, if no statistical significance is shown at the 0.05 level (2-sided) for the test of any specified endpoint in the hierarchical order, then that endpoint and all subsequent endpoints below this in the ranking order should not be considered statistically significant, regardless of their nominal p-value.

### 1. **Change from baseline in the frequency of headache days per 28-day period.**

This variable will be derived from the daily eDiary reports. It will be based on the count of headache days with at least 4 continuous hours in total duration of headaches, and/or headache of any duration with the use of migraine-specific acute headache medication(s) (ie, ergot alkaloids, ergot combinations, opioids, serotonin receptor agonists [“triptans”], or combination analgesics [simple analgesics combined with opioids or barbituates with or without caffeine]) days per 28-day period at Week 32.

The change from baseline in frequency of headache days will be compared between BOTOX and topiramate arms via analysis of covariance (ANCOVA) with baseline headache day count as the covariate. The estimated mean change from baseline and 95% CIs will be summarized for each treatment along with the 2-sided p-value. If the p-value is less than or equal to 0.05 then it will be considered as statistically significant and testing will continue to the next secondary efficacy analysis. The rules for data handling and missing value imputation will be the same as used for the primary endpoint.

### 2. **HIT-6 Score change from baseline**

The HIT-6 comprises 6 items that assess pain, role functioning, social functioning, cognitive functioning, vitality, and psychological distress. A total score is created by summing across all items, and ranges from 36 (no impact) to 78 (severe impact), reflecting a “best to worst” scoring. Score categories are based on the total score and include “little to no impact” (total score 36 to 49), “some impact” (total score 50 to 55), “substantial impact” (total score 56 to 59) and “severe impact” (total score 60 to 78). The continuous total score will be used in this analysis. The categorical HIT-6 scores will be summarized in a separate table.

The total HIT-6 score from the 28-day period collected at Week 30 will be compared between treatment arms using a nonparametric rank analysis of covariance (rank ANCOVA) (Stokes et al, 2000), with treatment as a factor and adjusting for the baseline value. If the p-value is less than or equal to 0.05, then it will be considered statistically significant and testing will continue to the final secondary efficacy analysis. The BLOCF method will be used for missing values for this endpoint.

3. **The proportion of patients with a  $\geq 70\%$  decrease from baseline in the frequency of headache days.**

The  $\geq 70\%$  responder rate will be analyzed using the same methods used to analyze the primary endpoint; a logistic regression model adjusted by the baseline frequency of headache days. Exact conditional logistic regression analysis will be performed if there are convergence issues with the default unconditional analysis. The rules for data handling and missing value imputation will be the same as used for the primary endpoint.

All secondary analyses will be repeated for the PP and ssITT Sets, if appropriate.

[REDACTED]

- [REDACTED]

[REDACTED]

- [REDACTED]

- [REDACTED]

■ [REDACTED]  
[REDACTED]  
[REDACTED]  
[REDACTED]

■ [REDACTED]  
[REDACTED]  
[REDACTED]  
[REDACTED]  
[REDACTED]  
[REDACTED]  
[REDACTED]  
[REDACTED]  
[REDACTED]

[REDACTED]

[REDACTED]	[REDACTED]
[REDACTED] [REDACTED] [REDACTED]	[REDACTED] [REDACTED] [REDACTED] [REDACTED] [REDACTED] [REDACTED] [REDACTED] [REDACTED] [REDACTED] [REDACTED]
[REDACTED] [REDACTED] [REDACTED]	[REDACTED] [REDACTED] [REDACTED] [REDACTED]

[REDACTED]  
[REDACTED]

[REDACTED]

[REDACTED]

[REDACTED] [REDACTED]	[REDACTED] [REDACTED]	[REDACTED] [REDACTED]	[REDACTED] [REDACTED]
[REDACTED] [REDACTED]	[REDACTED]	[REDACTED] [REDACTED]	[REDACTED] [REDACTED]

[REDACTED]	[REDACTED]	[REDACTED]	[REDACTED]
[REDACTED]	[REDACTED]	[REDACTED]	[REDACTED]
[REDACTED]	[REDACTED]	[REDACTED]	[REDACTED]
[REDACTED]	[REDACTED]	[REDACTED]	[REDACTED]
[REDACTED]	[REDACTED]	[REDACTED]	[REDACTED]
[REDACTED]	[REDACTED]	[REDACTED]	[REDACTED]
[REDACTED]	[REDACTED]	[REDACTED]	[REDACTED]
[REDACTED]	[REDACTED]	[REDACTED]	[REDACTED]

[REDACTED]

eDiary. The sum of the total scores will be divided by the number of MIBS-4 questionnaires taken over each 28-day period. The average continuous score will be used for this analysis.

The [REDACTED]  
[REDACTED]

[REDACTED]  
[REDACTED]  
[REDACTED]  
[REDACTED]

[REDACTED]  
[REDACTED]  
[REDACTED]

[REDACTED]  
[REDACTED]  
[REDACTED]  
[REDACTED]  
[REDACTED]

[REDACTED]  
[REDACTED]  
[REDACTED]  
[REDACTED]  
[REDACTED]

[REDACTED]  
[REDACTED]  
[REDACTED]  
[REDACTED]  
[REDACTED]  
[REDACTED]  
[REDACTED]  
[REDACTED]  
[REDACTED]

[REDACTED]	[REDACTED]		
[REDACTED]	[REDACTED]	[REDACTED]	[REDACTED]
[REDACTED]	[REDACTED]	[REDACTED]	[REDACTED]
[REDACTED]	[REDACTED]	[REDACTED]	[REDACTED]
[REDACTED]	[REDACTED]	[REDACTED]	[REDACTED]
[REDACTED]	[REDACTED]	[REDACTED]	[REDACTED]

[REDACTED]

[REDACTED]

[REDACTED]

## 9. Safety Analyses

All analyses of safety will be conducted using the Safety Set. All patients will be summarized according to the treatment they actually received, but the subgroup of topiramate patients who initially received topiramate and then switched to BOTOX will be summarized as follows:

- All safety assessments occurring prior to the date of the first dose of BOTOX will be summarized for the topiramate treatment arm.
- All safety assessments except AEs occurring on or after the date of the first dose of BOTOX will be summarized separately for the topiramate + BOTOX subgroup. For all AEs, the total number of patients (N) in each treatment arm will represent the number of patients that received that treatment. A patient may be counted in both treatment arms. The overall total will be the number of patients that received any treatment. The topiramate + BOTOX treatment arm will be a subset of the BOTOX treatment arm and will include patients that received both treatments. Denominators for percentages will be the total number of patients in each treatment arm or overall. Treatment-emergent AEs (TEAEs) include all AEs that start on or after the first dose of study medication up to the final visit, or are present prior to the first dose but increase in severity after the first dose of study medication up to the final visit. For patients who switch from topiramate to BOTOX, TEAEs starting on or after the date of the first BOTOX injection will be counted in the treatment arm that they are related to, as determined by a physician. If the TEAE is related to both treatments or if the relationship is unknown, it will be counted in both treatment arms but only once in the total. The topiramate + BOTOX subset will summarize all TEAEs that occurred after a patient has switched from topiramate to BOTOX.

Statistical hypothesis testing will not be performed on any safety results

